5.1. Summary of Study Design

Study RHBW is a Phase 3, multicenter, randomized, double-blind, placebo-controlled, parallel-group, outpatient study examining the efficacy and safety of 2 ixekizumab treatment regimens (80 mg every 2 weeks [Q2W] and 80 mg every 4 weeks [Q4W] subcutaneous [SC]), as compared to placebo SC in patients with active radiographic axial spondyloarthritis (rad-axSpA) who are tumor necrosis factor (TNF) inhibitor-experienced, during a double-blind, 16-week treatment period (Period 2). Starting doses of 80 mg and 160 mg (at Week 0) will be evaluated for each ixekizumab regimen.

Study RHBW will also evaluate long-term efficacy and safety of ixekizumab during the Extended Treatment Period (Period 3) for a total treatment duration of 1 year (52 weeks). Patients who complete Study RHBW may be eligible to enroll into a long-term study (Study I1F-MC-RHBY [RHBY]) for up to 2 additional years. Patients who do not enroll into Study RHBY will complete the Post-Treatment Follow-Up Period (Period 4) in Study RHBW.

[Figure RHBW.5.1](#) illustrates the study design.

Abbreviations: LV = last visit; LY = ixekizumab; n = number of patients; Q2W = every 2 weeks; Q4W = every 4 weeks; SC = subcutaneous; V = study visit; W = study week.

- a All patients will receive 2 injections at baseline, as detailed in Protocol Section 6.1. Patients randomized to an ixekizumab regimen will be randomized to a 160 mg starting dose or 80 mg starting dose at a 1:1 ratio (within each ixekizumab regimen).
- b All patients will receive 2 injections at Week 16, as detailed in Protocol Section 6.1. Patients randomized to placebo at Week 0 will begin ixekizumab 80 mg Q4W or ixekizumab 80 mg Q2W at Week 16 with a 160 mg starting dose (Protocol Section 6.1).
- c Patients who discontinue from study treatment for any reason and who have received at least 1 dose of investigational product will continue to the early termination visit (ETV) before entering the Post-Treatment Follow-Up Period. V801 and V802 are required for all patients; V803 may be needed depending on neutrophil counts (Protocol Section 6.1).

Figure RHBW.5.1. Illustration of study design for Clinical Protocol I1F-MC-RHBW.

5.2. Method of Assignment to Treatment

Patients who meet all criteria for enrollment will be randomized to double-blind treatment at Week 0 (Visit 2). Assignment to treatment groups will be determined by a computer-generated random sequence using an interactive web-response system (IWRS). The IWRS will be used to assign double-blind investigational product to each patient. Site personnel will confirm that they have located the correct assigned investigational product package by entering a confirmation number found on the package into the IWRS.

To achieve between-group comparability, the randomization will be stratified by country, baseline C-reactive protein (CRP) (nonelevated or elevated, elevated defined as >5.00 mg/L) and number of prior tumor necrosis factor (TNF) inhibitor used (1 or 2). Due to operational feasibility, stratification by CRP is based on the most recent CRP before randomization, (that is, screening CRP). The study will enroll approximately 60% of patients with elevated screening CRP (>5.00 mg/L) and approximately 40% of patients with nonelevated screening CRP (≤ 5.00 mg/L), and approximately 60% of patients with 1 prior TNF inhibitor and approximately 40% of patients with 2 prior TNF inhibitors.

5.3. Determination of Sample Size

Approximately 300 patients will be randomized at a 1:1:1 ratio in the Blinded Treatment Dosing Period (Period 2) to ixekizumab 80 mg Q2W, ixekizumab 80 mg Q4W, and placebo. With 100 patients per treatment group, CCI

these assumptions are based on the review of historical clinical studies in rad-axSpA (etanercept, adalimumab, infliximab, certolizumab, and golimumab [Davis et al. 2003; van der Heijde et al. 2005, 2006; Inman et al. 2008; Landewé et al. 2014]) and recent secukinumab data in patients who are TNF inhibitor experienced (Baeten et al. 2014; Sieper et al. 2014).

6. A Priori Statistical Methods

6.1. General Considerations

Statistical analysis of this study will be the responsibility of Eli Lilly and Company (Lilly). The statistical analyses will be performed using SAS® Version 9.2 or higher.

Continuous data will be summarized in terms of the number of observations, mean, standard deviation (SD), minimum, median, and maximum. The minimum and maximum will be reported to the same number of decimal places as the raw data recorded in the database. The mean and median will be reported to 1 more decimal place than the raw data recorded in the database. The SD will be reported to 2 more decimal places than the raw data recorded in the database. In general, the maximum number of decimal places reported shall be 4 for any summary statistic.

Categorical data will be summarized in terms of the number of patients in the analysis population, the number of patients providing data at the relevant time point, frequency counts, and the percentages corresponding to the appropriate method. Percentages will be presented to 1 decimal place. Percentages will not be presented for zero counts.

All confidence intervals (CIs) and statistical tests will be 2-sided unless otherwise specified. P-values which are ≥ 0.001 , and ≤ 0.999 , will be presented to 3 decimal places. All other p-values which are < 0.001 will be presented as < 0.001 , while p-values greater than 0.999 will be presented as > 0.999 . Confidence intervals (CIs) will be presented to 1 more decimal place than the raw data.

Age, sex, and race will be reported on all by-patient listings unless otherwise specified. Sex will be abbreviated as follows: female (F) and male (M). Race will be abbreviated as follows: American Indian or Alaska Native (AI), Asian (AS), Black or African American (BL), Native Hawaiian or other Pacific Islander (NH), White (WH), and Multiple (MU).

6.1.1. General Considerations for Analyses during the Blinded Treatment Dosing Period (Period 2)

Comparisons between each ixekizumab regimen (80 mg Q2W or 80 mg Q4W) and placebo will be performed for all analyses in Period 2.

Period 2 starts at the first injection of study treatment at Week 0 (Visit 2) and ends before the first injection of study treatment at Week 16 (Visit 8) or the early termination visit (ETV) (between Weeks 0 and 16).

Baseline will be defined as the last available value before the first injection for efficacy, health outcome, and safety analyses. In most cases, this will be the measure recorded at Week 0 (Visit 2). For efficacy measures, if the patient does not take any injection, the last available value on or before randomization date will be used. Change from baseline will be calculated as the visit value of interest minus the baseline value. For safety analyses using a baseline period, the baseline period is defined as the time from Visit 1 to the date/time of the first injection.

The randomization to treatment groups is stratified by country, screening CRP status (nonelevated versus elevated), and number of prior TNF inhibitors used (1 or 2) as described in Section 5.2. The countries will be categorized into geographic regions for analysis. Geographic regions are defined in Section 6.2. Unless otherwise specified, the statistical analysis models will adjust for geographic region, baseline CRP status, and number of prior TNF inhibitors used.

Unless otherwise specified, treatment groups of ixekizumab 80 mg Q2W and Q4W groups will be analyzed without regard to starting dose.

The primary analysis method for treatment comparisons of categorical efficacy and health outcomes variables at specific time points will be made using a logistic regression analysis with treatment, geographic region (Europe and non-Europe), number of prior TNF inhibitors used, and baseline CRP status in the model using PROC Logistic with a Wald test. The odds ratio and 95% CIs will be reported; treatment difference and 95% CI will also be reported. Secondary analysis will be conducted using a Fisher's exact test. In the case when the logistic regression model does not produce statistical results due to sparse data, Fisher's exact test will be used.

As a secondary analysis for the primary and major secondary categorical efficacy measures, a categorical, pseudo-likelihood based mixed-effects model of repeated measures (categorical mixed-effects model of repeated measures [MMRM]) estimating the percentage of patients achieving response across postbaseline visits may be used. The model will include treatment, geographic region, number of prior TNF inhibitors used, baseline CRP status, visit, and treatment-by-visit as fixed factors. The binomial distribution and the logit link will be used. The restricted maximum likelihood (REML) will be used. An unstructured covariance matrix will be used to model the within-patient variance-covariance errors. The Kenward-Roger approximation will be used to estimate the denominator degrees of freedom. The Newton-Raphson with ridging optimization technique will be used to aid with convergence. The probability of response, the corresponding 2-sided 95% CI, and the p-value for treatment comparisons at Week 16 (Visit 8) and all other postbaseline visits will be reported.

If the unstructured covariance matrix results in a lack of convergence, the heterogeneous Toeplitz covariance structure, followed by the heterogeneous autoregressive covariance structure, followed by the compound symmetry will be used. This order is specified according to a decreasing number of covariance parameters in the structure. The sandwich estimator (Diggle et al. 1994) for the covariance estimation will be used by specifying the EMPIRICAL option in SAS PROC MIXED. When sandwich estimation is used, the Kenward-Roger approximation for denominator degrees of freedom cannot be used. Instead, DDFM= BETWITHIN option will be used to estimate denominator degrees of freedom.

The primary analyses for continuous efficacy and health outcomes variables will be made using MMRM, except for magnetic resonance imaging (MRI) endpoints, which will be made using analysis of covariance (ANCOVA). A secondary analysis for continuous efficacy and health outcomes variables will be made using ANCOVA.

When the MMRM is used, the model will include treatment, geographic region, number of prior TNF inhibitors used, baseline CRP status, baseline value, visit, baseline value-by-visit, and

treatment-by-visit interaction as fixed factors (except for the analysis of CRP; see paragraph below). The covariance structure to model the within-patient errors will be unstructured. The REML will be used. The Kenward-Roger method will be used to estimate the denominator degrees of freedom. Type III tests for the least-squares (LS) means will be used for the statistical comparison; the 95% CI will also be reported. Treatment group comparisons with placebo at Week 16 (Visit 8) and all other visits will be reported. If the unstructured covariance matrix results in a lack of convergence, the similar approach specified above for categorical MMRM will be used.

For the analysis of CRP, the MMRM model will include treatment, geographic region, number of prior TNF inhibitors used, baseline CRP status, visit, and treatment-by-visit interaction as fixed factors. Note, for the ratio of postbaseline to baseline in CRP, analysis will be performed on the natural log transformed ratio. When the ANCOVA is used, the model will include treatment, geographic region, number of prior TNF inhibitors used, baseline CRP status, and baseline value (except for the analysis of CRP; see paragraph below). Type III sums of squares for the LS means will be used for the statistical comparison; the 95% CI will also be reported.

For the analysis of CRP, the ANCOVA model will include treatment, geographic region, number of prior TNF inhibitors used, and baseline CRP status. Note, for the ratio of postbaseline to baseline in CRP, analysis will be performed on the natural log transformed ratio.

For the analysis of Ankylosing Spondylitis Disease Activity Score (ASDAS) disease activity states (that is, inactive, low, high, and very high disease states), the repeated measures proportional odds model will include treatment, geographic region, number of prior TNF inhibitors used, baseline CRP status, visit, and treatment-by-visit interaction.

The impact of ixekizumab starting dose of 160 mg versus 80 mg on treatment response at Week 16 and time to onset of action will be summarized and evaluated. Response rates in categorical variables (including ASAS40 and ASAS20) and LS mean change in continuous efficacy measure of CRP at Week 16 will be presented for patients randomized to ixekizumab Q2W or Q4W treatment regimen with ixekizumab 160-mg starting dose and with ixekizumab 80-mg starting dose.

For response rates, starting dose comparisons within ixekizumab Q2W or Q4W treatment regimens will be based on a logistic regression model with treatment, starting dose, and treatment-by-starting-dose interaction (only ixekizumab Q2W and Q4W will be included in the analyses). Starting dose comparison combining ixekizumab Q2W and Q4W treatment regimens will be based on a logistic regression model with only starting dose in the model.

For mean change analysis, starting dose comparisons within ixekizumab Q2W or Q4W treatment regimens will be based on a MMRM model with treatment, starting dose, baseline value, visit, baseline value-by-visit, treatment-by-visit, treatment-by-starting dose, starting dose-by-visit, and treatment-by-starting dose-by-visit interactions as fixed factors. Starting dose comparison combining ixekizumab Q2W and Q4W treatment regimens will be based on a MMRM model with starting dose, baseline value, visit, baseline value-by-visit, and starting dose-by-visit

interaction as fixed factors. The differences in response rates and LS mean changes between starting doses and the corresponding 95% CI will be reported as well.

Time-to-onset analyses will focus on earlier time points (for example, Weeks 1, 2, 4, and so on) for abovementioned response variables in a similar fashion. For time-to-first-clinical-response analysis, starting dose comparisons within and across ixekizumab Q2W and Q4W treatment regimens will be based on a log-rank test.

For variables that are not collected at each postbaseline visit, data may exist at visits where the variable was not scheduled to be collected, due to early discontinuation visits. In these situations, data from the early discontinuation visit that do not correspond to the planned collection schedule will be excluded from the MMRM and categorical MMRM analyses (Andersen and Millen 2013). However, the data will still be used in other analyses, including shift analyses, change from baseline to last-observation carried forward (LOCF) or modified baseline observation carried forward (mBOCF) endpoint analyses, and other categorical analyses.

For selective continuous efficacy variables, percent improvement will be calculated as $100 \times (\text{baseline score} - \text{observed scores}) / \text{baseline score}$, unless specified otherwise. If a patient has experienced an improvement, this measure will be positive. If a patient has experienced a worsening, this measure will be negative.

Figures showing the proportion of patients achieving a categorical clinical response at each scheduled visit within each treatment group may be provided.

Time to first clinical response (for example, ASAS40) will be assessed based on the intent-to-treat (ITT) population in Period 2. Unless specified otherwise, time to first clinical response (for example, ASAS40) is defined as:

Time to first clinical response (days) = Date of first clinical response during Period 2 – Date of Week 0 randomization + 1

If a patient has not met the criteria for response by completion or early discontinuation of Period 2, the patient will be censored at the date of their last visit during Period 2.

The number of patients at risk and experiencing a response by each scheduled visit during Period 2 will be presented by treatment group. The Kaplan-Meier estimate of the proportion of patients achieving the clinical response will be presented for each visit. Treatment group comparisons will be performed using the log-rank test and the log-rank test stratified by geographic region, number of prior TNF inhibitors used, and baseline CRP status. A Kaplan-Meier plot of the time to first clinical response by treatment group will also be provided.

Fisher's exact test will be used for all adverse events (AE), baseline, discontinuation, and other categorical safety data. Continuous vital sign and laboratory values will be analyzed by an ANCOVA with treatment and baseline value in the model.

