As a secondary analysis for the primary and major secondary categorical efficacy measures, a categorical mixed-effects model of repeated measures (categorical MMRM) estimating the percentage of patients achieving response across postbaseline visits may be used. The model will include treatment, geographic region, baseline CRP status, number of prior TNF inhibitors used, visit, and treatment-by-visit as fixed factors, as well as the continuous, fixed covariate of baseline value and baseline value-by-visit interaction (when appropriate). The binomial distribution and the logit link will be used. An unstructured covariance matrix will be used to model the within-patient variance-covariance errors. The Kenward-Roger approximation will be used to estimate the denominator degrees of freedom. The Newton-Raphson with ridging optimization technique will be used to aid with convergence. The probability of response, the corresponding 2-sided 95% CI, and the p-value for treatment comparisons at Week 16 (Visit 8) and all other postbaseline visits will be reported.

If the unstructured covariance matrix results in a lack of convergence, the heterogeneous Toeplitz covariance structure, followed by the heterogeneous autoregressive covariance structure, followed by the compound symmetry, will be used. This order is specified according to a decreasing number of covariance parameters in the structure. The sandwich estimator (Diggle et al. 1994) for the covariance estimation will be used by specifying the EMPIRICAL option in SAS PROC MIXED. When sandwich estimation is used, the Kenward-Roger approximation for denominator degrees of freedom cannot be used. Instead, the DDFM=BETWITHIN option will be used to estimate denominator degrees of freedom.

The primary analyses for continuous efficacy and health outcomes variables will be made using MMRM. A secondary analysis for continuous efficacy and health outcomes variables will be made using analysis of covariance (ANCOVA).

When the MMRM is used, the model will include treatment, geographic region, baseline CRP status, number of prior TNF inhibitors used, baseline value, baseline value-by-visit, visit, and treatment-by-visit interaction as fixed factors. The covariance structure to model the

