within-patient errors will be unstructured. If the unstructured covariance matrix results in a lack of convergence, the similar approach specified above for categorical MMRM will be used. The Kenward-Roger method will be used to estimate the denominator degrees of freedom. Type III tests for the least-squares (LS) means will be used for the statistical comparison; the 95% CI will also be reported. Treatment group comparisons with placebo at Week 16 (Visit 8) and all other visits will be tested.

When the ANCOVA is used, the model will include treatment, geographic region, baseline CRP status, number of prior TNF inhibitors used, and baseline value. Type III sums of squares for the LS means will be used for the statistical comparison; the 95% CI will also be reported.

The impact of ixekizumab starting dose of 160 mg versus 80 mg on time-to-onset (focus on Week 4) and treatment response during the Period 2 (focus on Week 16) will be summarized and evaluated; details will be specified in the SAP.

For variables that are not collected at each postbaseline visit, data may exist at visits where the variable was not scheduled to be collected, due to early discontinuation visits. In these situations, data from the early discontinuation visit that do not correspond to the planned collection schedule will be excluded from the MMRM and categorical MMRM analyses. However, the data will still be used in other analyses, including shift analyses, change from baseline to last observation carried forward (LOCF) or modified baseline observation carried forward (mBOCF) endpoint analyses and other categorical analyses.

Fisher's exact test will be used for all AE, baseline, discontinuation, and other categorical safety data. Continuous vital sign and laboratory values will be analyzed by an ANCOVA with treatment and baseline value in the model.

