#### **9.4.2.2. Other Secondary Efficacy Analyses**

There will be no adjustment for multiple comparisons. Analyses will be conducted for the other secondary efficacy objectives defined in Section 3. Specific details of analyses will be specified in the SAP.

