CRP	CRP change from baseline; ratio of postbaseline to baseline CRP	MMRM	ITT Population	IXE80Q2W & IXE80Q4W vs. placebo at Week 16 and all other postbaseline visits in Period 2	Other secondary efficacy analyses (Section 6.10.4)
		ANCOVA with mBOCF	ITT Population	IXE80Q2W & IXE80Q4W vs. placebo at Week 16 and all other postbaseline visits in Period 2	Other secondary efficacy analyses (Section 6.10.4)
		MMRM	ITT Population	IXE80Q2W & IXE80Q4W Starting Dose 160 mg and 80 mg during Period 2	Other secondary efficacy analyses (Section 6.10.4)
		Descriptive statistics of change from baseline	Extended Treatment Period Population	No treatment group comparisons during Period 3	Other secondary efficacy analyses (Section 6.10.4)

Measure	Variable	Analysis Method (Sections 6.1, 6.3)	Population (Section 6.1.5)	Comparison/Time Point	Analysis Type
Mobility-Related Measures	BASMI linear (incl. 5 components); chest expansion, occiput to wall distance change from baseline	MMRM	ITT Population	IXE80Q2W & IXE80Q4W vs. placebo at Week 16 and all other postbaseline visits in Period 2	Other secondary efficacy analyses (Section 6.10.4)
		ANCOVA with mBOCF	ITT Population	IXE80Q2W & IXE80Q4W vs. placebo at Week 16 and all other postbaseline visits in Period 2	Other secondary efficacy analyses (Section 6.10.4)
		Descriptive statistics of change from baseline	Extended Treatment Period Population	No treatment group comparisons during Period 3	Other secondary efficacy analyses (Section 6.10.4)
Enthesitis Scores	MASES and SPARCC change from baseline	MMRM	ITT Population with Baseline MASES >0(or SPARCC >0)	IXE80Q2W & IXE80Q4W vs. placebo at Week 16 and all other postbaseline visits in Period 2	Other secondary efficacy analyses (Section 6.10.4)
		ANCOVA with mBOCF	ITT Population with Baseline MASES >0(or SPARCC >0)	IXE80Q2W & IXE80Q4W vs. placebo at Week 16 and all other postbaseline visits in Period 2	Other secondary efficacy analyses (Section 6.10.4)
		Descriptive statistics of change from baseline	Extended Treatment Period Population with Baseline MASES >0(or SPARCC >0)	No treatment group comparisons during Period 3	Other secondary efficacy analyses (Section 6.10.4)
	MASES score = 0 (similarly SPARCC = 0)	Logistic regression analysis with NRI; Fisher's exact test with NRI	ITT Population with Baseline MASES >0(or SPARCC >0)	IXE80Q2W & IXE80Q4W vs. placebo at Week 16 and all other postbaseline visits in Period 2	Other secondary efficacy analyses (Section 6.10.4)

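### The CRP models leave out the continuous baseline CRP value without a stated reason, which costs precision on an other secondary endpoint

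*SAP*

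**What the plan says.** SAP 6.1.1 sets a general MMRM and a general ANCOVA for continuous endpoints, both with the baseline value, and attaches the same exception to each: "except for the analysis of CRP; see paragraph below". The CRP versions follow. For the MMRM: "For the analysis of CRP, the MMRM model will include treatment, geographic region, number of prior TNF inhibitors used, baseline CRP status, visit, and treatment-by-visit". For the ANCOVA: "For the analysis of CRP, the ANCOVA model will include treatment, geographic region, number of prior TNF inhibitors used, and baseline CRP status". Table RHBW.6.5 applies these models on two scales: "CRP change from baseline; ratio of postbaseline to baseline CRP". The ratio is analysed after a natural-log transformation.

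The protocol's general models in section 9.2.1 have no CRP exception. Its MMRM reads "When the MMRM is used, the model will include treatment, geographic region, baseline CRP status, number of prior TNF inhibitors used, baseline value, baseline value-by-visit", and its ANCOVA reads "When the ANCOVA is used, the model will include treatment, geographic region, baseline CRP status, number of prior TNF inhibitors used, and baseline value". Section 9.4.2.2 of the protocol leaves room for the SAP to refine other secondary analyses: "Specific details of analyses will be specified in the SAP".

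The starting-dose comparison in SAP 6.1.1 also covers CRP: "LS mean change in continuous efficacy measure of CRP at Week 16 will be presented". Its MMRM contains the baseline value and the baseline-by-visit interaction, but not CRP status.

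**The concern.** CRP is measured as a continuous variable at baseline in every patient, yet the ixekizumab-versus-placebo models use only whether it lies above or below 5 mg/L. Change scores and log ratios stay correlated with baseline unless the slope of follow-up on baseline is exactly 1. Within each CRP stratum, baseline therefore still explains part of the outcome variance, and that part is left in the residual.

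The SAP also treats baseline CRP in two ways. It conditions on the continuous value when comparing starting doses, but not when comparing drug with placebo. The two models belong to different families, so this is not a contradiction, but the difference is unexplained. The revision history for Version 2 says only that the CRP analysis was clarified.

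At stake is the width of the confidence intervals for the CRP effect. No primary or major secondary conclusion depends on it.

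**Working it through.** **The plan's own figures.** Neither document gives an SD, a correlation or an expected effect for CRP. The only design figure is the roughly 96% power for ASAS40 in the protocol synopsis (27% versus 7%, 100 per arm, two-sided Fisher test at 0.05). Exact enumeration gives 96.5%, so it reproduces, but it does not bear on CRP.

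**Inputs from the documents.** 100 patients per arm; elevated CRP defined as above 5.00 mg/L; about 60% of patients elevated (SAP 5.2 and 5.3). The 60% refers to screening CRP and is assumed to hold at baseline.

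**Assumed inputs.** Log-normal CRP, log-SD 1.0 to 1.2, baseline-to-Week-16 correlation r of 0.5 to 0.7 on the log scale, and a proportional drug effect of 0, 25% or 50% reduction.

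**Log ratio, closed form.** For a normal variable split 60/40, the two-level factor explains c = φ(z)²/(0.6 × 0.4) = 0.622 of the log-baseline variance, leaving w = 1 − 0.622 = 0.378. With equal log variances σ² at both times, the slope of the log ratio on log baseline is r − 1. Hence:

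- residual variance with continuous baseline: σ²(1 − r²)
- residual variance with status only: σ²(1 − r²) + w(1 − r)²σ²
- ratio: 1 + w(1 − r)/(1 + r)

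At r = 0.5 this is 1 + 0.378 × 0.5/1.5 = 1.13. At r = 0.7 it is 1 + 0.378 × 0.3/1.7 = 1.07. At r = 0.5, 100 patients per arm act like 100/1.126 ≈ 89, and a comparison with 80% power falls to about 75%.

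The result is sensitive to the equal-variance assumption. If the post-baseline log-SD is k times the baseline log-SD, the ratio becomes 1 + w(1 − rk)²/[k²(1 − r²)]. For k from 0.7 to 1.2 and r from 0.3 to 0.7, the increase in standard error runs from 24% down to under 1%.

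**Simulation, both scales.** 4,000 two-arm trials per scenario, single-visit ANCOVA, CRP status alone versus status plus baseline (raw baseline for raw change, log baseline for the ratio). Region and number of prior TNF inhibitors were left out of both models.

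| log-SD, r | Raw variance ratio: no effect / 25% / 50% | Raw power at 25%: status only → with baseline | Raw power at 50% | Log-ratio power at 25% |
|---|---|---|---|---|
| 1.0, 0.5 | 1.50 / 1.69 / 1.95 | 0.285 → 0.432 | 0.814 → 0.980 | 0.595 → 0.643 |
| 1.0, 0.7 | 1.32 / 1.55 / 1.79 | 0.384 → 0.520 | 0.913 → 0.995 | 0.787 → 0.816 |
| 1.2, 0.5 | 1.64 / 1.72 / 2.07 | 0.169 → 0.276 | 0.572 → 0.867 | 0.447 → 0.494 |
| 1.2, 0.7 | 1.48 / 1.69 / 1.88 | 0.234 → 0.338 | 0.718 → 0.934 | 0.626 → 0.651 |

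Log-ratio variance ratios were 1.05 to 1.13 over all 12 scenarios, in line with the closed form. At a 50% reduction, log-ratio power was at least 99% with either model. Type I error with status only was 4.2% to 5.2%, consistent with no bias.

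A separate three-arm simulation (2,000 runs per setting, r from 0.3 to 0.7, log effects of 0.5 and 1.0) gave raw-scale standard errors 28% to 53% larger without the baseline value.

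**The case against.** The strongest reply is that this is a deliberate, fully prespecified choice with little at stake.

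- **Explanation.** The exception is flagged twice and each CRP model is written out, so a programmer has no latitude. Protocol 9.2 requires an amendment only for changes to principal features and places the justification for other changes in the study report. This stands, and there is no protocol breach. It answers only the missing reason, not the lost precision.
- **Overlap.** CRP is the one endpoint whose baseline is already in the model in dichotomised form. Each CRP model, including the starting-dose one, carries exactly one baseline-CRP term. That may be the motive, but it is no bar: the protocol fits both terms, and the SAP's ASDAS model fits CRP status beside a baseline score that itself contains log CRP.
- **Size.** On the log scale, which suits skewed data, the standard error grows by only about 2.5% to 6% under the main assumptions. This stands.
- **Raw scale.** The raw-change figures depend on heavy log-normal tails. Under a proportional effect, a common-slope model is itself misspecified. The size is therefore uncertain, but randomisation keeps the adjusted estimate valid whether or not the slope is right.
- **Timing.** Version 4 of the SAP is dated after the version approved before first unblinding. A change to Period 2 covariates now would have to be labelled accordingly. This also stands.

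**Conclusion.** The concern holds. Both CRP models drop an available baseline covariate that the protocol's general models and the SAP's covariate rule include, and no reason is stated.

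The consequence is precision only. It is modest for the log ratio: about 5 to 12 of 100 patients per arm in effective sample size, and 2.5 to 5 points of power at a 25% reduction. It is larger for raw change, the form in which the objectives list the endpoint. That the omission exists, and that adding baseline helps, is certain enough to act on. The size rests on the assumed SD, correlation and distribution and should be read as a range.

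CRP is an other secondary endpoint without multiplicity adjustment, so the primary and major secondary results are untouched. This should be corrected, but it does not threaten the trial.

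**What to change.** In SAP 6.1.1, add log baseline CRP to the log-ratio models and baseline CRP to the raw-change models. Include the baseline-by-visit interaction in the MMRM and keep CRP status as a factor. If Week 16 data are already unblinded, report this as a labelled supplementary analysis beside the prespecified one. If the omission is to stay, state the reason in 6.1.1 and reconcile it with the starting-dose CRP model and with section 6.2.

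The cost is two sentences and a few degrees of freedom. The data are already collected at Visit 2, and Table RHBW.6.4 names Visit 1 as the fallback.
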